3.1 Analysis Populations

The primary population includes all randomized patients, with the exception of one individual who fled from the ETU on the first day. This is the only subject for whom there is missing primary outcome data. (Sensitivity analyses will also be performed including this individual in his/her assigned group, as described below).

The primary analyses will be performed on all subjects regardless of baseline covariates. The study stratified randomization based on cycle threshold (CT > 22 vs. CT \leq 22) and geographic location, and analyses will be presented accordingly. In addition, some analyses will specify age subgroups defined as: adults \geq 18 years vs. children aged <18 years.

3.2 Subject Accrual

The following information about accrual will be summarized:

- Number randomized: overall and by month/year. Dates of first and last randomizations.
- Number randomized by geographic location (United States, Liberia, Sierra Leone, Guinea), country, and site
- Number randomized by cycle threshold (CT ≤ 22 versus > 22)
- Number randomized by children versus adults

3.3 Eligibility violations

Number (N) and percent (%) of any participants who were enrolled in violation of inclusion/exclusion criteria will be reported for each inclusion/exclusion criterion separately and total. Reports will be overall, by geographic location (United States vs. West Africa) and by treatment site.

Listing: Description of violations of eligibility criteria among randomized subjects.

3.4 Baseline Characteristics

The following baseline data will be summarized overall and by treatment assignment, geographic location (United States, Liberia, Sierra Leone and Guinea) and treatment center:

- Demographics: Age, sex, race, country of birth, work involving contact with a person with Ebola or decedents (N and %), and role (e.g., doctor, nurse, ambulance driver, laboratory) and enrollment in any other studies related to Ebola
- Clinical information: Results of pregnancy test, weight, height, blood pressure, pulse, body temperature, respiratory rate and oxygen saturation
- Illness information: days since onset of symptoms, cycle threshold (actual value and dichotomized as CT > 22 vs. CT ≤ 22), country where EVD diagnosis was confirmed
- Symptoms: Fever, sore throat, cough, etc.
- Chemistries: measurement of serum creatinine and potassium were required, all other chemistries were considered optional. Optional data will be summarized for subjects where data is available.
- Hematology and Coagulation: optional data summarized as provided.
- Urinalysis: optional data, summarized for subjects where data is available.
- Imaging and Resuscitation: optional data, summarized for subjects where data is available.

3.5 Data Completeness

The following reports will be provided overall and by treatment assignment, geographic location and treatment center:

- Withdrawal of consent (N and %)
- Required forms:
 - Number (and % of expected) of completed baseline forms
 - Number (and % of expected) for each item on the baseline form
 - Number (and % of expected) of daily follow-up forms (overall and by study day)
 - Number (and % of expected) for each item on the daily follow-up form (overall and by study day)
 - Number (and % of expected) of current symptom forms (overall and by study day)
 - Number (and % of expected) for each item on the daily follow-up form (overall and by study day)
 - Number (and % of expected) of daily chemistries forms
 - Number (and % of expected) for each item on the daily chemistries form (overall and by study day)
 - Number (and % of expected) of ZMapp forms (overall and by study day)
 - Number (and % of expected) of completed day 28 forms received, according to the following categories: completed, still in follow-up period, withdrawn and lost to follow-up

- Number (and % of expected) of completed day 58 forms received, according to the following categories: completed, still in follow-up period, withdrawn and lost to follow-up
- Number (and % of expected) of discharge forms
- Number (and % of expected) of death forms
- Optional forms:
 - o Number (and % of maximum possible) of completed daily hematology forms
 - o Number (and % of maximum possible) of daily urinalysis forms
 - \circ $\;$ Number (and % of maximum possible) of daily resuscitation forms

3.6 Optimized Supportive Care Descriptions

- Optimized supportive care provided by study day:
 - Intravenous fluids as total volume (continuous variable) and % receiving fluids
 - Intravenous fluids will also be presented by combining all fluids (normal saline and lactated ringers, etc) and presenting in ml/kg to adjust for differences in age and body mass.
 - Other treatments (electrolytes, ventilation, ECMO, supplemental oxygen, medications etc.) as %
- The number of days with supportive care infusions until discharge/death will be summarized.
- Also, for 3-day windows: 1-3, days, 4-6 days, etc. supportive care infusions will be summarized.
- Data will be analyzed both by geographic region and, where applicable, by incorporation of Favipiravir as oSOC.

3.7 ZMapp Infusion Summaries

Note: for patients assigned to the ZMapp group, ZMapp was to be started immediately following randomization. The 2nd dose was to be given 3 days after the 1st dose; the 3rd dose was to be given 3 days after the 2nd dose.

- The distribution of the number of infusions per patient (0, 1, 2, 3)
- Time elapsed between randomization and first dose
- Study day of infusion of each dose will be summarized
- Duration (minutes and mean) by study day
 - additional separate tables for adults and children
- Volume received (mean and ml/kg) by study day.
- Percent receiving prepared volumes of 95% or greater.
- Calculated dose (mg/kg) of ZMapp Dose actually administered
- Number and percent of patients experiencing infusion reactions
 - o Total N (%)
 - \circ N (%) categorized by the specific infusion reactions reported
 - N (%) which required intervention
 - N% by intervention taken
- Number and percent of patients experiencing infusion interruptions

- Total N (%)
- Pre-treatments administered before infusions to ameliorate reactions
- Other problems with the infusion noted on the case report form.
- Listing of other problems related to infusion
- Listing of subjects assigned to ZMapp who did not receive all doses before death: subject ID, site, days from randomization to first dose, days from first ZMapp to death, total doses given

3.8 Primary Outcome

The primary outcome is death within 28 days from randomization, and the primary population includes all randomized patients, with the exception of one individual who fled from the ETU on the first day and for whom no other primary data were subsequently captured.

Note: as a sensitivity analysis to assess the impact of the single subject with unknown vital status following randomization, the primary analysis described below will be performed assuming the subject was alive at 28 days and repeated assuming the subject was dead at 28 days.

Primary analysis

Inference relating to the primary endpoint will quantify the probability that the 28-day mortality rate is lower (or higher) under ZMapp relative to oSOC using the Bayesian paradigm as follows:

- A. The prior distribution of 28-day mortality probabilities, p₀ and p₁, in the oSOC and ZMapp arms is that of independent uniforms on [0,1].
- B. The posterior distributions of p₀ and p₁ after observing x₀ and x₁ deaths among n₀ and n₁ people in the two arms is that of independent betas with respective parameters (x₀+1, n₀-x₀+1) and (x₁+1, n₁-x₁+1).
- C. The posterior probability that p₁<p₀ will be computed: if this probability is 0.975 or greater, ZMapp will be declared superior to oSOC, whereas if the probability is 0.025 or less, ZMapp will be declared inferior to oSOC.
- D. Treatment effect estimates and 95% credible intervals will be computed for both the relative risk p_1/p_0 and absolute risk difference p_1-p_0 . The medians of the posterior distributions of p_1/p_0 and p_1-p_0 are used to estimate these quantities. 95% credible intervals are computed as follows.
 - a. For p_1/p_0 , compute lower and upper limits (L and U, respectively) satisfying $P(p_1/p_0 \le L \text{ given } x_0, x_1) = 0.025$ and $P(p_1/p_0 \ge U \text{ given } x_0, x_1) = 0.025$.
 - b. For p₁-p₀, compute lower and upper limits (L and U, respectively) satisfying P(p₁-p₀<L given x₀,x₁)=0.025 and P(p₁-p₀>U given x₀,x₁)=0.025.

Additional Supportive Analyses Using Primary Outcome:

Alternative test statistics:

The following alternative test statistics will be performed on the primary outcome as secondary analyses.

- Barnard's unconditional test will be performed using a one-tailed test of p₁=p₀ versus p₁<p₀.
 - A. The first alpha level used is 0.025 (one-sided). As with the Bayesian analysis, the overall type 1 error rate including monitoring may exceed 0.025.
 - B. The second alpha level is adjusted using the Haybittle-Peto monitoring procedure:

 α =0.025-(0.001)k, where k is the number of interim looks at the data.

A confidence interval will be computed for the absolute risk difference using Barnard test methodology and confidence level $1-2\alpha$. This will be done for each of the two alpha levels specified above.

- The same approach specified above for Barnard's test, including the two separate alpha levels, will also be performed for Fisher's exact test. A confidence interval for the odds ratio will be computed using the non-central hypergeometric distribution.
- An analysis of time to death will be performed using a log-rank test. In addition, a stratified log-rank test will be performed with 4 strata defined by location and cycle threshold. (See description of stratification variables below). This will be done for each of the two alpha levels specified above. Tests of treatment by subgroup interaction will be performed.

Stratification and subgroup analyses

- Additional analyses will be performed within two strata defined by cycle threshold: ≤22 versus >22 for all subjects. To assess whether there is a treatment by cycle threshold interaction, we will compute the posterior probability that the treatment effect (absolute or relative) differs by cycle threshold.
- Analysis combining the United States, Liberia, and Sierra Leone as one location stratum, while Guinea constitutes the other location stratum. (The standard of care in Guinea typically included favipiravir, which was not the case in the other countries). Note that the protocol initially specified stratified randomization for the USA. However, only one patient in the USA was randomized, which is why the location strata have been changed to USA/Liberia/Sierra Leone vs Guinea. To assess whether there is a treatment by location interaction, we will compute the posterior probability that the treatment effect (absolute or relative) differs by location. An additional sensitivity analysis will exclude the lone patient treated in the United States. The treatment effect within the United States versus West Africa could make interpretation of results more difficult. For example, if the patient was assigned to oSOC and survived, that may simply reflect better oSOC in the United States.

The following baseline predictors will be considered: age, gender, geographic location, CT value, duration of symptoms at enrollment, and type of symptoms (e.g.: systemic symptoms [fever, myalgias, arthalgias], fluid loss [diarrhea, vomiting, blood loss], respiratory compromise [SOB, hypoxia, elevated respiratory rate >24, supplemental oxygen requirement], hemodynamic instability [systolic BP <90, pulse >100, pressor support requirement], renal compromise [anuria, serum creatinine > 2x ULN], and CNS compromise [confusion, seizures, coma]. We hypothesize based on these analyses that benefits of ZMapp on mortality (compared to oSOC) will be greater among patients with a medium to low risk of early (1st 3 days) death, relative to those for whom it is high. Since there may be some patients who enter the trial with a very low risk of death (e.g., no matter the intervention, they were likely to survive), we also hypothesize that the benefits of ZMapp on mortality (compared to oSOC) will be greater among patients whose risk of death *within 8* days is medium or high compared to those from whom it is low.

Figures:

- Forest plots of above mortality rates according to the following subgroups:
 - · CT≤22/>22
 - Geographic area
 - · Adults vs children
 - ' Sex
 - · Duration of time from onset of symptoms to randomization
 - Baseline risk stratification score (as defined above)
- Kaplan-Meier plots will be made for the following:

- · Treatment group
- · Treatment group and adults and children
- Treatment group and CT ≤22 versus >22 for all subjects
- Treatment group and duration of time from onset of symptoms to randomization

3.9 Secondary Outcomes

Major secondary outcomes:

This section prioritizes the secondary analyses. The study has limited power—the end of the epidemic means the study will close prior to accruing its targeted sample size. As a result, prioritization of secondary endpoints is needed. We also feel it is important to carefully consider the strengths and limitations of the secondary outcomes prior to unblinding. It is recognized that the secondary endpoint analyses described below will be difficult to interpret if the primary analysis does not demonstrate that ZMapp significantly reduces mortality compared to oSOC alone.

Two endpoints are under consideration: time-to-viral clearance (clearance is defined as the first negative PCR result) and time-to-discharge. One could give different arguments for which is a better choice. Time to discharge undoubtedly encompasses several aspects simultaneously: clearance of virus, amelioration of symptoms, etc. However, there is the possibility of a treatment-associated bias in this outcome. For example, if some patients who were given ZMapp were discharged later to make sure there were no drug-related safety issues, then ZMapp may appear less favorable using this endpoint. Also, we have heard reports that patients were kept in a treatment unit after recovery for a variety of reasons, including waiting for discharge kits containing food supplies and other household items or the presence of a relative undergoing treatment for Ebola at the same unit. These issues make time-to-discharge a less precise indication of how a patient feels or functions.

Time-to-viral clearance is a more objective outcome, but it is also not free of problems. Specifically, it is unclear whether this assay was adequately standardized across sites in this study, leading to concerns about measurement variability. Further, samples were taken on half or fewer of participants on many of the days. Nonetheless, failure to measure PCR is likely to have occurred equally in the two arms and the time interval between a positive and negative PCR was within 3 days for 39 of 50 patients (78%) and within 5 days for 47/50 (94%) of patients . Therefore, it is felt that **time to viral clearance should be the more important secondary outcome**, although both outcomes will be analyzed. Note that, for either outcome, death must be taken into account.

1. Viral clearance/death

Unless otherwise stated, viral clearance is defined by the occurrence of a negative PCR.

A. The first analysis of viral clearance/death is a rank test in which patients who die within 28 days receive worse ranks than survivors, with earlier deaths given worse ranks than later deaths. Among 28-day survivors, patients with longer times to viral clearance will be given worse ranks. Average ranks will be used in the case of ties. A permutation test will be used to determine a p-value for this test.

An additional analysis will use the van Elteren stratified Wilcoxon test on the four strata defined by location (USA/Liberia/Sierra Leone versus Guinea) and cycle threshold (≤22 versus >22). An interaction test will be conducted to determine whether the treatment effect differs by each of these subgroups, and subgroups defined by age, gender, and duration from onset of symptoms to randomization. Subgroup results will be presented using a forest plot. [Ref: Van Elteren, P.H. (1960). On the combination of independent two-sample tests of Wilcoxon. *Bulletin of the International Statistical Institute* **37**, 351-361.]

B. The second analysis of viral clearance/death is based on Fisher's exact test with outcome being death or time to viral clearance exceeding 10 days (i.e., 11 or more days). The rationale for this secondary analysis is as follows. It may be that ZMapp prevents very long times to viral clearance, but has no effect on intermediate times. If we knew the right threshold constituting a "long time to viral clearance," we would select that number. To determine the appropriate threshold, we examined data blinded to treatment assignment. If we select a threshold that is too small, then exceeding the threshold may not represent a bad outcome. On the other hand, if the threshold is too large, the number of people exceeding it may be very small. In that case, the test of whether the proportion of people dead or with large time to viral clearance differs by treatment arm will be nearly the same as the test of whether the proportion of people dead differs by treatment arm. Therefore, the key is to choose a threshold that is among the higher times, but not so high that very few people exceed it. Figure 1 (below) shows the plot of days to viral clearance. Approximately one quarter (13/49=26.5%) of the observations are longer than 10 days. This threshold seems to balance the above concerns. Therefore, the second analysis of viral clearance/death will use Fisher's exact test on outcome: death within 28 days or time to viral clearance exceeding 10 days (i.e., 11 or more days). Note that Fisher's exact test is a permutation test, and permutation tests remain valid even if the threshold is determined after examining blinded data.

An additional analysis will use the Mantel-Haenszel estimator and test to stratify by the 4 strata defined by location (USA/Liberia/Sierra Leone versus Guinea) and cycle threshold (≤22 versus >22). An interaction test will be conducted to determine whether the treatment effect differs by each of these subgroups, and subgroups defined by age, gender, and duration from onset of symptoms to randomization. Subgroup results will be presented using a forest plot.

[figure not shown]
2. Discharge/Death

A. The first analysis of discharge/death will be the same rank-based method as for viral clearance/death, but substituting "discharge" for "viral clearance." An unstratified and stratified test (van Elteren test) will be performed, where the four strata are defined by location (USA/Liberia/Sierra Leone versus Guinea) and cycle threshold (<22 versus >22).

B. The second analysis of discharge/death uses Fisher's exact test with outcome being death or time to discharge exceeding 16 days (i.e., 17 or more days). The rational for this threshold is as follows. Figure 2 (below) is a blinded display of times to discharge. A threshold of greater than

16 days again separates approximately the highest 25% of times (13/49=26.5%). This threshold is also a reasonable choice to minimize overlap between this analysis and that of time to viral clearance. Figure 3 (below) shows the threshold lines (plotted at 10.5 for time to viral clearance and 16.5 for time to discharge). Although there is substantial overlap, represented by the upper right region, there are also 5 people meeting the >10 days to viral clearance, but not the >16 days to discharge. Likewise, there are 5 people meeting the >16 days to discharge, but not the >10 days to viral clearance.

As with the corresponding analysis of time to viral clearance, a stratified analysis will also be performed using the Mantel-Haenszel estimator and test on the four strata defined by location (USA/Liberia/Sierra Leone versus Guinea) and cycle threshold (≤22 versus >22). An interaction test will be conducted to determine whether the treatment effect differs by each of these subgroups, and subgroups defined by age, gender, and duration from onset of symptoms to randomization. Subgroup results will be presented using a forest plot.

Days to Viral Clearance

Figure 1. Distribution of days to viral clearance for all subjects who cleared Ebola virus

[figure not shown]

Figure 2. Distribution of days to discharge for all discharged subjects

[figure not shown]

Figure 3. Scatter plot of days to discharge versus days to viral clearance for all surviving subjects

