21.4.2 Baseline Laboratory Testing

When possible, the following tests will be performed and recorded as baseline determinations. Baseline laboratory testing shall be performed within 24 hours of study entry (randomization).

21.4.2.1 Minimum Baseline Requirements:

- Creatinine
- Potassium
- Ebola PCR with threshold cycle (ct)
 - Although any positive Ebola PCR collected up to 10 days prior to informed consent provides eligibility, a baseline specimen should be collected on Day 0 if the prior specimen was collected >24 hours, as the viral load may have substantially changed.

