В	4/6/15	Clarification of the site- specific considerations have been added to the protocol (section 6.15) based on the resources available. Further information from Liberian Ebola Treatment Units has preliminarily identified a correlation between baseline Cycle Threshold (CT) value on Ebola PCR and patient outcomes. This has prompted the Study Team to change the stratification for the randomization procedures of this study
C	4/20/15	The main purposes of the amendment are to acknowledge that the ability of individual sites to perform full spectrum of clinical research components outlined in prior versions protocol varied widely depending upon such factors as staffing, available equipment, and current operational, clinical, and safety practices. Therefore this version of the protocol

SUMMARY of AMENDMENTS TO PROTOCOL

		attempts to define the minimal standards for assessment of efficacy and safety as well as allow full detailed assessments to obtain full longitudinal data collection when sites are able.
D	7/13/15	An updated Investigator's Brochure and an updated version of the ZMAPP Patient Information Sheet was added which will be given to participants at the time of consent.
E	11/23/15	Added long-term follow-up. The DSMB strongly recommended long-term follow-up of enrolled subjects be considered (within reasonable limits of access and feasibility) given reports of the recurrence of Ebola virus disease in some patients. Interested subjects will be offered the opportunity, where and whenever feasible, to participate in long term follow-up (up to 1 year or more depending upon need) past Day 58 of their illness in order to determine whether they are at risk for late onset of any history or symptoms consistent with delayed virologic relapse potentially arising from immunologically-privileged sites.

Data Analysis Plan for MCM RCT

1	STU	JDY OVERVIEW								
2	SUN	JMMARY OF REPORTS								
3	OPE 3.1 3.2 3.3 3.4	Accru Eligib Baseli	4 4 4 5							
4	CLC	CLOSED REPORT TO THE DSMB								
	4.1	1 BASELINE CHARACTERISTICS								
	4.2	DATA (Completeness	6						
	4.3	PRIMA	RY OUTCOME	6						
		4.3.1	Primary analysis at study completion	6						
		4.3.2	Additional analyses	8						
	4.4	Secondary Outcomes								
		4.4.1	Overall Survival	8						
		4.4.2	Time-to-viral load clearance	8						
		4.4.3	Daily Outcomes	9						
	4.5	SAFETY OUTCOMES								
		4.5.1	SAEs							
		4.5.2	Safety listings							
		4.5.3	Pregnancies							
		4.5.4	Infusion Reactions							

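### The lead test of viral clearance/death leaves baseline CT unused; it is valid, but loses power if CT is prognostic, and adjusting for CT and location before unblinding would recover it.

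*Combined protocol and SAP*

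**What the plan says.** Section 3.9 of the Final Data Analysis Plan (Final DAP) weighs time to viral clearance against time to discharge and concludes that "time to viral clearance should be the more important secondary outcome". Part 1A then sets the tests:

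- **Lead test.** "The first analysis of viral clearance/death is a rank test in which patients who die within 28 days receive worse ranks than survivors", with survivors ranked by time to clearance. "A permutation test will be used to determine a p-value for this test". No covariate or stratum is named, and nothing says whether treatment labels are permuted within the randomisation strata. Part 2A carries the same method over to discharge/death and calls for an unstratified and a stratified version, which confirms that the lead test is unstratified.
- **Added test.** "An additional analysis will use the van Elteren stratified Wilcoxon test on the four strata defined by location" (USA/Liberia/Sierra Leone versus Guinea) and by CT cut at 22. Interaction tests and a forest plot follow.

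On CT itself:

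- Protocol section 22 (Design) and Final DAP 3.1 make it a randomisation factor.
- Protocol section 21.4.2 lists it among the minimum baseline tests.
- Final DAP 3.4 summarises both its actual value and the split.
- Amendment B adopted it as a stratification factor because information from Liberian treatment units "has preliminarily identified a correlation between baseline Cycle Threshold (CT) value on Ebola PCR and patient outcomes".

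No section adjusts viral clearance for CT as a continuous value.

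**The concern.** Baseline CT is the starting value of the quantity whose clearance is being timed, so it is the natural covariate. When randomisation is stratified on a prognostic factor, the arms are closer to balance on it than simple randomisation would make them. A reference distribution that ignores the strata then overstates the variance of the test statistic, and the test rejects too seldom. Splitting CT at 22 can also discard information within each half. Final DAP 3.9 says power is limited because the epidemic ended early (72 randomised against a maximum of 200), so the most important secondary comparison may be giving up power that the recorded data could supply.

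**Working it through.** **1. The plan's own figure.** The documents give no power, effect size or alpha for this test. The nearest stated figure is primary-endpoint power of 83% at 100 per arm, mortality 0.30 v 0.50. By formula: null SE = sqrt(2 x 0.4 x 0.6/100) = 0.0693; alternative SE = sqrt((0.21 + 0.25)/100) = 0.0678; power = Phi[(0.20 - 1.96 x 0.0693)/0.0678] = Phi(0.947) = 82.8%. Simulating the Bayesian boundary gives 83.3%. The figure reproduces, but it does not bear on the secondary test.

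**2. Inputs.** From the documents: 72 randomised 1:1 (Final DAP 2 and 3.1), of whom 71 have the primary outcome; CT and location strata. Assumed: the correlation rho between CT and outcome, the treatment effect, the share at CT 22 or below (40%) and about 30% deaths.

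**3. What the cut keeps.** For a normal covariate with a linear effect, a split at centile q keeps phi(c)^2/[q(1 - q)] of the explained variance, where c is the normal quantile of q. At q = 0.40: 0.3863^2/0.24 = 0.622. At q = 0.25 and 0.50 the shares are 0.54 and 0.64. At rho = 0.5 the effective sample size is 72/(1 - 0.25) = 96.0 with continuous CT and 72/(1 - 0.622 x 0.25) = 85.3 with the split.

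**4. Size of the lead test if permutation ignores the strata.** The true variance is about (1 - 0.622 rho^2) of the assumed variance. At rho = 0.5 this factor is 0.8445, so size = 2[1 - Phi(1.96/sqrt(0.8445))] = 2[1 - Phi(2.133)] = 3.3%; simulation also gave 3.3%. At rho = 0.3 it is 4.4% (simulated 4.0%). At rho = 0 it is 5%.

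**5. Power, two-sided 5%, graded CT effect.** Simulation A: 71 patients, logistic death model (treatment log-odds -0.8), clearance time about 26% shorter, van Elteren on CT only. Simulation B: 72 patients, 0.6 SD latent effect, van Elteren on CT x location, rank regression on CT and location. Simulation C: a separate run on the same lines as B.

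| Simulation, rho | Unstratified | Permuted within strata | van Elteren | Continuous CT |
|---|---|---|---|---|
| A, 0 | 75% | - | 75% | 75% |
| B, 0.2 | 68% | - | 68% | 70% |
| A, 0.3 | 71% | - | 73% | 75% |
| B, 0.3 | 69% | - | 68% | 72% |
| C, 0.3 | 68% | 70% | 68% | 71% |
| A, 0.5 | 66% | - | 72% | 77% |
| B, 0.5 | 70% | - | 73% | 79% |
| C, 0.5 | 70% | 76% | 75% | 80% |
| B, 0.6 | 70% | - | 77% | 84% |

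A further run of B that added within-stratum permutation gave 70/75/74/79% at 0.5. At 0.5, continuous CT therefore gains 9 to 11 points over the lead test, and roughly half of that comes from respecting the strata.

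**6. Sensitivity.** If the CT effect is a pure step at 22 (rho 0.5), power is 72% unstratified, 80% van Elteren and 78% continuous. If CT has reliability 0.7 (rho 0.5, graded), it is 70%, 72% and 76%.

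**The case against.** The strongest reply is that most of this is already covered. Randomisation balances CT, the four-stratum van Elteren test and a CT interaction test are pre-specified in the same section, and no alpha or gatekeeping depends on which test comes first. The plan itself warns that secondary results will be hard to interpret if mortality is not reduced. All of that stands, and it is why this is an optional improvement.

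Four stronger readings are tempting, and the documents do not support them:

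- *The lead test is the weakest valid option.* Analysis B of the same outcome, Fisher's exact test on death or clearance beyond 10 days, is weaker. A simulation on the lines of A, with its own assumed intercept and spread, gave about 40% for Fisher against 60% for the rank test at correlation 0.5, and 47% against 65% at 0.3. At 0.2 to 0.3, simulation B shows van Elteren no better than the lead test.
- *The lead test has a true size of about 3%.* Only if permutation ignores the strata, and the plan does not say. Within-stratum permutation brings the size back to about 5%.
- *Cutting CT at 22 must lose power.* Not if risk steps there; the split then does slightly better than continuous CT.
- *CT is known to be strongly prognostic for clearance.* Amendment B reports a preliminary correlation with patient outcomes. It gives no size and does not mention viral clearance.

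The plan also doubts that the PCR assay was standardised across sites, which weakens continuous CT as a covariate. That reduces the gain without removing it, and it is a reason to adjust for location as well.

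**Conclusion.** The point holds as a matter of efficiency. The lead test is valid and unbiased, but it does not use a prognostic factor that the trial stratified on and recorded. Against a test adjusted for continuous CT, the cost is nil at correlation 0, about 1 to 4 points of power at 0.3 or less, and about 9 to 11 points at 0.5. These figures assume that permutation ignores the strata and that the CT effect is graded. About half the loss at 0.5 is recovered by permuting within strata or by the van Elteren test already planned. The further gain from continuous CT over the cut, about 2 to 7 points for correlations of 0.2 to 0.6, needs a graded effect and shrinks with assay noise. The correlation, treatment effect and share at CT 22 or below are all assumptions, so the size is a range. Priority is low.

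**What to change.** Before unblinding, make the lead test for viral clearance/death a rank test of the composite, adjusted for the rank of continuous baseline CT and for location (USA/Liberia/Sierra Leone v Guinea), with treatment permuted within the CT x location strata. Do the same for discharge/death. Keep the unstratified and four-stratum van Elteren tests as supportive.

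State the permutation strata explicitly. Protocol section 22 stratified on western Africa versus United States/Europe, and Final DAP 3.8 regroups location because only one patient was randomised in the USA. The proposal follows the regrouped definition, as the planned van Elteren test does.

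Add a simple rule for a missing baseline CT, since protocol section 21.4.2 asks for baseline tests only when possible. The team could check the pooled correlation between CT and the composite while blinded, just as it chose the 10-day threshold from blinded data.

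The cost is a paragraph of plan wording and a few lines of code, with no new data. The downside is a slightly less familiar test statistic.
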